538 via phone or email, or by completion of the appropriate eCRFs as applicable. If the form(s) are not
539 initially completed, they should be completed as soon as possible after there is sufficient information to
540 evaluate the event. All other reportable ADEs and other reportable AEs should be submitted by
541 completion on the eCRF(s) within 7 days of the site becoming aware of the event.

542 The Sponsor will notify all participating investigators of any adverse event that is serious, related, and
543 unexpected. Notification will be made within 10 working days after the Sponsor becomes aware of the
544 event.

545 Each principal investigator is responsible for reporting serious study-related adverse events and abiding
546 by any other reporting requirements specific to his/her Institutional Review Board or Ethics Committee.

547 Upon receipt of a qualifying event, the Sponsor will investigate the event to determine if a UADE has
548 occurred, and if indicated, report the results of the investigation to the HDEC, and Medsafe within 10
549 working days of the Sponsor becoming aware of the UADE. The Sponsor must determine if the UADE
550 presents an unreasonable risk to participants. If so, the Sponsor must ensure that all investigations, or
551 parts of investigations presenting that risk, are terminated as soon as possible but no later than 5 working
552 days after the Sponsor makes this determination and no later than 15 working days after first receipt
553 notice of the UADE.

554 The investigators are also required to report, without unjustified delay, all device complaints and
555 malfunctions that could have led to a UADE, including device complaints and malfunctions, irrespective
556 of whether an adverse event occurred.

557 **6.5 Safety Oversight**

558 The study Sponsor's Medical Director or Chief Medical Officer will serve as Medical Monitor, and will
559 review all reported adverse events, including all cases of severe hypoglycemia and DKA, and adverse
560 device effects that are reported during the study. SAEs typically will be reviewed within 1 working day of
561 reporting. Other AEs typically will be reviewed on a weekly basis.

562 The Medical Monitor will confirm the MedDRA code assigned and adjudicate events as specified in the
563 safety management plan for relatedness to the study procedure and investigational device, assess
564 seriousness and severity, and determine if the event the event is anticipated or unanticipated. Both the
565 investigators and Medical Monitor's assessments will be recorded, however, the adjudication decision of
566 the Medical Monitor will be used for the final classification of events, including relatedness to the study
567 procedures and/or the investigational device, for the determination of safety endpoints and for all
568 regulatory reports, product labeling, and publications or presentations. If there has been a discrepancy
569 between the Medical Monitor and Coordinating Investigator when classifying an AE, it will be reported to
570 HDEC.

571 **6.6 Stopping Criteria**

572 **6.6.1 Participant Discontinuation of Study Device**

573 In the case of an unanticipated system malfunction resulting in a severe hypoglycemia or DKA event
574 (or a malfunction that could have led to severe hypoglycemia or DKA), use of the study device will be
575 suspended for that participant while the problem is diagnosed.

576 In the absence of a device malfunction, use of the study device by a participant will be discontinued if
577 any of the following occur:

- 578 • The investigator believes it is unsafe for the participant to continue on the intervention. This could be
579 due to the development of a new medical condition or worsening of an existing condition; or
580 participant behavior contrary to the indications for use of the device that imposes on the participant's
581 safety
- 582 • The participant requests that the treatment be stopped
- 583 • Participant pregnancy
- 584 • One distinct episode of DKA in the study treatment period as defined in section 6.2.4
- 585 • One distinct severe hypoglycemia event in the study treatment period as defined in section 6.2.3

586 Each DKA or severe hypoglycemia event will be reviewed by the Medical Monitor with respect to
587 determination of cause and whether the occurrence of the event can be attributed to use of the study
588 device.

589 **6.6.2 Criteria for Suspending or Stopping Overall Study**

590 In addition to the suspension of device use due to a UADE as described in section 6.6.1, study activities
591 could be similarly suspended if the manufacturer of any constituent study device requires stoppage of
592 device use for safety reasons (e.g. product recall). The affected study activities may resume if the
593 underlying problem can be corrected by a protocol or system modification that will not invalidate the
594 results obtained prior to suspension.

595 Closed-loop system use will also be suspended if there are three or more cases of severe hypoglycemia or
596 three or more cases of DKA across the entire study in participants who have initiated Tandem Freedom
597 use. The HDEC and Medsafe will be notified. After assessment of the problem and any corrections are
598 implemented, use of the closed-loop system may be restarted if approval is received from the HDEC and
599 Medsafe.

600

601

Chapter 7: Miscellaneous Considerations

602

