BG confirmed >16.7 mmol/L for more than 2 hours and ketones are ≥ 0.6 mmol/L	
A manual correction bolus may be delivered via injection to assure proper absorption in the setting of likely infusion set failure. The decision to give a manual correction bolus by injection may be adjusted by investigator discretion, based on insulin-on-board and clinical judgement.
 
Fingerstick BG and ketone measurements will be repeated after approximately 1 hour.
 
After a manual correction bolus, the study staff will replace the participant's infusion set, if they believe it is contributing to the hyperglycemia, with a new infusion set and the correction bolus will be repeated per the investigator's discretion. Closed loop will be disabled by the investigator for the next 4 hours and until BG has returned to <10 mmol/L.

Participant loses consciousness or has a seizure, or participant is unable to take oral carbohydrates	1 mg of IM glucagon or 3 mg nasal glucagon will be administered and 911 will be called. The study will be stopped immediately until sponsor conducts a full investigation to determine the root cause for the compromised system performance and is able to address all issues. Sponsor will also communicate the results of this root cause investigation to regulatory bodies and to study investigators.

252

253 Meal boluses and all interaction with the pump will be supervised by study staff to ensure that the correct
254 number of carbohydrate grams are entered into the bolus calculator and the correct dose is given.

255 When meal boluses are given, participants will give the bolus per their usual meal bolus timing, but not
256 more than 15 minutes before the meal.

257 At least one member of the study medical staff (Physician, NP, PA, or other qualified clinician) will
258 always be present on site.

259 During the study session, participants may change their study sensor or their infusion site as needed
260 per their usual care. Participants will be encouraged to use TruSteel infusion sets for the duration of the
261 study.

262 Insulin and glucose data from the screening visit, as well as follow up visits and at the start of the hotel
263 session, will be reviewed and the site investigator may adjust insulin delivery profile settings as needed in
264 accordance with their clinical practice.

265 **3.2.2 Day 1**

266 Following the Control-IQ run-in phase, participants will commence the hotel supervised phase.

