- 425 • evaluation or treatment was obtained at a health care provider facility for an acute event involving
426 hypoglycemia, or the participant contacted the site and received guidance following the occurrence of
427 an acute event involving hypoglycemia

428 When a severe hypoglycemia event occurs (as defined above), an Adverse Event Form should be
429 completed. Severe hypoglycemia events should be considered to be serious adverse events with respect to
430 reporting requirements. When a severe hypoglycemia event occurs during use of a study device, it
431 generally will be considered to be unrelated to the device (per section 6.2.5) if the device functioned as
432 intended and there does not appear to be a flaw in how the device is intended to function.

433 **6.2.4 Hyperglycemic/Ketotic Events**

434 Hyperglycemia is only reportable as an adverse event when one of the following criteria is met:

- 435 • the event involved DKA, as defined by the Diabetes Control and Complications Trial (DCCT) and
436 described below
- 437 • evaluation or treatment was obtained at a health care provider facility for an acute event involving
438 hyperglycemia or ketosis, or the participant contacted the site and received guidance on how to
439 manage the hyperglycemia/ketosis
- 440 • blood ketone level ≥ 1.0 mmol/L, even if there was no communication with a health care provider at
441 the time of the event

442 Hyperglycemic events are classified as DKA if all of the following are present, or judged likely to have
443 been present based on available data:

- 444 • Symptoms such as polyuria, polydipsia, nausea, or vomiting;
- 445 • Serum ketones > 1.5 mmol/L or large/moderate urine ketones;
- 446 • Either arterial blood pH < 7.30 or venous pH < 7.24 or serum bicarbonate (or CO₂) < 15 ; and
- 447 • Treatment provided in a health care facility

448 When a hyperglycemia/ketotic event qualifies as an AE, or as a SAE as defined in section 6.2.1, an
449 Adverse Event Form should be completed. Events meeting DKA criteria should be considered to be
450 serious adverse events with respect to reporting requirements. Hyperglycemia events not meeting criteria

451 for DKA generally will not be considered as serious adverse events unless one of the SAE criteria in
452 section 6.2.1 is met.

453 When a hyperglycemia/DKA event occurs during use of a study device, it generally will be considered to

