8.4 Outcome Measures

651

The two study periods are:

652

1) Control-IQ at home run-in period.

653

2) The Tandem Freedom hotel observed period.

654

Primary Endpoints for each period:

655

1. Severe hypoglycemia (with cognitive impairment such that assistance of another individual is needed for treatment)

657

2. Number of diabetic ketoacidosis events

658

Secondary Endpoints for each period:

659

1. All device-related adverse events

660

2. CGM hypoglycemia outcomes

661

a. Overall % time <3.0 mmol/L

662

b. Overall % time <3.9 mmol/L

663

3. Times in ranges-overall (3.9-10 mmol/L, >10 mmol/L, >13.9 mmol/L, 3.9-7.9 mmol/L)

664

4. Mean glucose

665

5. Overall variability (CV and SD)

666

Due to the small sample size and feasibility nature of the study, primarily descriptive statistics will be used.

668

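### DKA counts only if treated in a health care facility, so a ketoacidosis treated wholly at the hotel would, as written, be missing from the primary count and the one-episode trigger

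*Combined protocol and SAP*

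**What the plan says.** Section 6.2.4 introduces the definition with "Hyperglycemic events are classified as DKA if all of the following are present, or judged likely to have" been so on the available data. Four items follow: symptoms; serum ketones above 1.5 mmol/L or moderate to large urine ketones; acidosis, given as "Either arterial blood pH < 7.30 or venous pH < 7.24 or serum bicarbonate (or CO₂) < 15"; and "Treatment provided in a health care facility". The protocol defines DKA nowhere else and does not define a health care facility.

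Three places use the term:
- Section 8.4 lists "Number of diabetic ketoacidosis events" as the second primary endpoint, for each period, without a definition of its own.
- Section 6.6.1 discontinues the device for a participant after "One distinct episode of DKA in the study treatment period as defined in section 6.2.4".
- Section 6.6.2 suspends closed-loop use after "three or more cases of DKA across the entire study in participants who have initiated Tandem Freedom" use, with no cross-reference to 6.2.4.

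On the setting, section 3.2.1 puts the Freedom period in a hotel and states "At least one member of the study medical staff (Physician, NP, PA, or other qualified clinician) will" be there at all times. In Table 1, the row for confirmed glucose above 16.7 mmol/L for more than 2 hours with ketones of at least 0.6 mmol/L says "A manual correction bolus may be delivered via injection to assure proper absorption in the setting of likely infusion set failure". It adds retesting, infusion set replacement if staff think the set is contributing, and temporary disabling of closed loop. That row has no upper ketone limit and no transfer step.

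**The concern.** The place of treatment is a required part of a primary safety endpoint, and the investigational period is held somewhere that is not obviously a health care facility but is staffed to treat ketosis. Two events with the same physiology could be classified differently because one participant was driven to a hospital and the other was treated in the hotel.

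Three things depend on the classification. One is the primary DKA count for the Freedom period. Another is the participant-level trigger, which uses 6.2.4 by name. The third is seriousness: events meeting the DKA criteria are serious for reporting purposes, while other ketotic events generally are not unless a criterion in 6.2.1 is met. Under section 6.4 that can decide between 1 working day, for an SAE possibly related to the study, and 7 days. The other primary endpoint, severe hypoglycemia, has no place-of-treatment condition.

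**Working it through.** The plan states no event rate, power or alpha for this endpoint, so there is no figure to reproduce. The check is a reading of the text, followed by a sense of scale.

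**Tracing one event.** Take a hotel participant with symptoms, ketones above 1.5 mmol/L and acidosis, treated only by study clinicians.

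1. Symptoms: met.
2. Ketones: met, and measurable with the meter in use (section 4.1.3).
3. Acidosis: pH and bicarbonate are not among the hotel procedures in section 3.2 or the laboratory tests in Chapter 5. Without a sample, this item can be met only through the clause that allows inference from available data.
4. Place of treatment: not met. The inference clause does not help, because where the participant was treated is known.

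The event therefore adds 0 to the count in 8.4 and 0 to the trigger in 6.6.1. It adds 0 to the three-case rule in 6.6.2 only if that rule uses 6.2.4, which is likely because no other definition exists, but is not stated.

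**Effect on the result.** Section 8.3 asks for at least 10 completers. With n = 10, one reclassified event moves the result from 0/10 to 1/10. If none is counted, the one-sided 95% upper bound on the risk per participant is 1 − 0.05^(1/10) = 0.259. For n = 20, the most that may be enrolled, it is 1 − 0.05^(1/20) = 0.139. As the definition stands, these bounds describe facility-treated DKA only.

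**Illustration for the triggers.** Let p be the true risk per participant of an event meeting criteria 1 to 3, and c the share of such events treated in a facility. Both are assumptions; the documents give neither. With at most one event per participant and independence, the number counted is Binomial(10, pc). Then P(at least 1) = 1 − (1 − pc)^10, and P(at least 3) is the upper binomial tail. The last column applies only if 6.6.2 uses 6.2.4.

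| p | c | P(at least 1 counted) | P(at least 3 counted) |
|---|---|---|---|
| 0.05 | 1 | 0.401 | 0.012 |
| 0.05 | 0.5 | 0.224 | 0.002 |
| 0.10 | 1 | 0.651 | 0.070 |
| 0.10 | 0.5 | 0.401 | 0.012 |
| 0.20 | 1 | 0.893 | 0.322 |
| 0.20 | 0.5 | 0.651 | 0.070 |
| any | 0 | 0 | 0 |

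The table shows how the counts depend on c. It does not predict rates: section 1.1.2 reports no DKA in the prior study of ten adults.

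**The case against.** The strongest reply is that the affected case is narrow and the safety net is wide. Most of this stands.

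- **Acidosis is required.** A reader might infer that symptoms with ketones above 1.5 mmol/L, treated at the hotel, are an uncounted DKA. They are not: without the third criterion the event is ketosis and is rightly left out. Because the hotel has no planned pH or bicarbonate test, measuring either would probably mean a transfer, after which the fourth criterion could be met. The gap is the event whose acidosis is inferred and whose treatment never leaves the hotel.
- **On-site treatment of DKA is not prescribed.** The Table 1 row is discretionary, starts at 0.6 mmol/L and does not mention DKA. Nothing in it prevents transfer.
- **The term is open.** The study safety plan in the Protocol Summary once describes the hotel phase as inpatient, and under section 6.5 the Medical Monitor makes the final classification, following a safety management plan that is not in the document. The Monitor might accept the hotel as a facility. But no section says so, and 6.2.4 itself distinguishes care at a provider facility from guidance given by the site.
- **The event is not lost.** Blood ketones of 1.0 mmol/L or more are a reportable adverse event. The event may be serious under 6.2.1. Section 6.6.1 also provides for stopping when the investigator thinks continuing is unsafe, and for suspension after a malfunction that could have led to DKA. These safeguards do not enter the primary count and do not operate through the DKA trigger.

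A further tempting reading is that the definition favours Freedom because a run-in event at home would go to a facility and be counted. The documents do not support it. Section 3.1 lets participants contact study providers at any time, and 6.2.4 foresees site guidance on managing ketosis. An event handled that way fails the same criterion. Detection is also closer in the hotel, with 24-hour monitoring and ketone checks in confirmed prolonged hyperglycemia.

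**Conclusion.** The point holds in a limited form. On the plain text, an event meeting criteria 1 to 3 and treated wholly at the hotel is excluded from the primary DKA count and from the one-episode trigger. This rests on two assumptions: that the hotel is not a health care facility, which no section settles, and that the participant is not transferred. The link to 6.6.1 is explicit. The link to 8.4 follows because 6.2.4 is the only definition. The link to 6.6.2 is an inference.

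The likely size is one event at most, 0/10 against 1/10, in a study that section 8.2 describes as descriptive and without hypotheses. The direction of any difference between periods is unknown. Nor do the documents support saying that such an event escapes safety oversight. What remains is an ambiguity in a primary safety endpoint that should be closed before an event occurs, so that the classification is not decided after the fact.

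**What to change.** Three changes to the text, none of which alters treatment:

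1. Keep the 6.2.4 count as the stated endpoint. Add to the safety table, for both periods, one row counting events that meet criteria 1 to 3, present or inferred by the Medical Monitor, regardless of place of treatment.
2. State, before the first hotel session, how treatment by study clinicians at the hotel is classified under the fourth criterion.
3. Reconcile Table 1 in 3.2.1 with 6.2.4, 6.6.1, 6.6.2 and 8.4, so that it is explicit which definition of DKA the endpoint and each trigger use. Which one the triggers should use is for the sponsor and the clinical team; no clinical or stopping rule is proposed here.

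The cost is a sentence or two and one table row. Little new data should be needed, since any event with blood ketones above 1.5 mmol/L already exceeds the 1.0 mmol/L reporting threshold. The downside is that the extra count relies more on judgement, because acidosis will often be inferred, and it may look slightly less favourable. Showing it beside the unchanged 6.2.4 count keeps comparability with studies that use that definition.

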Protocol Identifying Number:	TP-0020402
Protocol Name:	Tandem Freedom Feasibility Trial #2
Protocol Version / Date:	1.0 / 20 NOV 2024

The Principal Investigators (undersigned) hereby declare that they have read this protocol and agree to its contents.

The investigator agrees that the study will be conducted according to the applicable New Zealand regulations (Medsafe and Health and Disability Ethics Committee), International Conference on Harmonization (ICH) guidelines on Good Clinical Practice (GCP) and the principles of the World Medical Association Declaration of Helsinki 2008. The investigator will conduct all aspects of this study in accordance with all national, state, and local laws or regulations.

By written consent to this protocol, the investigators agree to the above and to fully co-operate with all monitoring and audits in relation to this trial by allowing direct access to all documentation, including source data, by authorized individuals representing Tandem Diabetes Care, Inc., HDEC, Medsafe New Zealand, and/or by the US Federal, State and local regulatory authorities.

Investigator Name: _____

Investigator Signature: _____

Date (DD/MMM/YYYY): _____

PROTOCOL SUMMARY

[figure not shown]
Study Sponsor	Tandem Diabetes Care, Inc.
Protocol Number	TP-0020402
Protocol Title	Tandem Freedom Feasibility Trial #2
Précis	This feasibility study is a prospective, single arm study evaluating the Tandem Freedom system compared to a Control-IQ technology run-in phase in adults with type 1 diabetes. Existing Control-IQ technology users will use Control-IQ technology at home for 1 week, then will use Tandem Freedom in a supervised hotel setting with Dexcom follow active. The goal of Tandem Freedom is to use the system without requiring meal boluses.
Products	Investigational Device: t:slim X2 insulin pump with Tandem Freedom Algorithm
Objectives	The objective of the study is to assess the feasibility of the Tandem Freedom system, by assessing safety and performance in a short-term supervised setting in adults with type 1 diabetes under direct clinical supervision.
Number of Sites	1 Clinical Site in New Zealand
Study Design	Single arm, prospective feasibility study to assess safety.
Number of Participants	Up to 20 participants signing consent to use the study devices, with a goal that at least 10 complete the study.

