454 be unrelated to the device (per section 6.2.5) if the device functioned as intended and there does not
455 appear to be a flaw in how the device is intended to function.

456 **6.2.5 Relationship of Adverse Event to Study Investigational Device**

457 The study investigator will assess the relationship of any adverse event to the study device or study drug.
458 The Medical Monitor also will make this assessment, which may or may not agree with that of the study
459 investigator. Reporting requirements will be based on the Medical Monitor's assessment.

460 To ensure consistency of adverse event causality assessments, investigators should apply the following
461 general guidelines when determining whether an adverse event is related to a study device or study drug:

462 **Unrelated:** The AE is clearly not related to a study drug/device and a likely alternative etiology exists
463 such as an underlying disease, environmental or toxic factors or other therapy.

464 **Unlikely Related:** The AE does not follow a reasonable temporal sequence during or after use of study
465 drug/device and a more likely alternative etiology exists such as an underlying disease, environmental or
466 toxic factors, or other therapy.

467 **Possibly Related:** The AE occurred in a reasonable time during or after use of study drug/device; but
468 could be related to another factor such as an underlying disease, environmental or toxic factors, or other
469 therapy; and there is a possible, though weak, scientific basis for establishing a causal association
470 between the AE and the study drug/device.

471 **Probably Related:** The AE occurred in a reasonable time during or after use of study drug/device; is
472 unlikely to be related to another factor such as an underlying disease, environmental or toxic factors, or
473 other therapy; and there is a plausible, though not strong, scientific basis for establishing a causal
474 association between the AE and the study drug/device.

475 **Definitely Related:** The AE occurred in a reasonable time during or after use of study drug/device;
476 cannot be explained by another factor such as an underlying disease, environmental or toxic factors, or
477 therapy; and there is a strong scientific basis for establishing a causal association between the AE and the
478 study drug/device.

479 Events determined to be *Possibly Related*, *Probably Related*, or *Definitely Related* will be considered

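### The sponsor's own medical officer has the final say on device-relatedness, and the investigator's recorded view has no planned place in the results

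*Combined protocol and SAP*

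**What the plan says.** The rule is in Section 6.5 (Safety Oversight), with supporting text in 6.2.3 to 6.2.5 and Chapter 8.

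- **Who adjudicates.** "The study Sponsor's Medical Director or Chief Medical Officer will serve as Medical Monitor, and will" review all reported adverse events.
- **What happens to the two views.** Both are kept: "investigators and Medical Monitor's assessments will be recorded, however, the adjudication decision of" the Medical Monitor prevails. The sentence goes on that "the Medical Monitor will be used for the final classification of events, including relatedness to the study" and then "procedures and/or the investigational device, for the determination of safety endpoints and for all" regulatory reports, labeling and publications.
- **Reporting.** Section 6.2.5 accepts that the Medical Monitor may disagree with the "investigator. Reporting requirements will be based on the Medical Monitor's assessment".
- **Disagreements.** Section 6.5 provides that where there is a discrepancy "between the Medical Monitor and Coordinating Investigator when classifying an AE, it will be reported to" HDEC. It gives no other use for a discrepancy.
- **Default on relatedness.** Sections 6.2.3 and 6.2.4 say that severe hypoglycemia, hyperglycemia or DKA during device use will generally be treated as unrelated when the device worked as designed and shows no apparent flaw in that design.
- **Analysis.** Section 8.4 names "All device-related adverse events" as the first secondary endpoint for each period. Section 8.1 tabulates events and participants. Nothing in Chapter 8 tabulates by the investigator's assessment or lists disagreements.
- **Design.** The Protocol Summary describes a "Single arm, prospective feasibility study to assess safety". No masking, independent adjudicator, adjudication committee or data safety monitoring board is described.

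**The concern.** Safety is the study's primary objective (Section 8.2). The final call on whether the device contributed to an event rests with an officer of its manufacturer. In a single-arm study with a known change of pump, that officer cannot be unaware of which system was running. The investigator's staff are on site throughout the hotel period and are better placed to see the circumstances of an event. Their assessment is collected but leaves no trace in the endpoint tables when it differs.

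The default in 6.2.3 and 6.2.4 sharpens this. It turns on whether the algorithm's intended function is flawed, and the final judge of that question works for the company that makes it. The label also has a practical consequence: under 6.2.9, among serious events only related ones and UADEs are followed after a participant finishes, while data collection on other events stops at completion.

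Few events are likely. Section 1.1.2 reports that the earlier ten-person study had no severe hypoglycemia, no DKA and no serious adverse event. A single classification may therefore decide whether the summary reads as some device-related events or none, and a reader of the results could not tell that the two assessors had differed.

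**Working it through.** The plan gives no figure to reproduce: there are no hypotheses (8.2) and no power analysis (8.3). The check is therefore which endpoints the adjudication rule can move.

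**Step 1. What the Medical Monitor adjudicates.** Section 6.5 lists relatedness to procedure and device, seriousness, severity, and whether the event was anticipated. It then gives the Medical Monitor the final classification of events in general terms.

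**Step 2. What each endpoint in 8.4 depends on.**

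- *Device-related adverse events (secondary 1).* This depends directly on relatedness. Section 6.2.5 has five grades and treats possibly, probably and definitely as related for HDEC and Medsafe reporting. Section 8.4 states no cut of its own. If the same cut applies, a one-grade difference between unlikely and possibly puts an event in or out of the endpoint.
- *Severe hypoglycemia and DKA (primary).* These are counted whatever the relatedness, seriousness or severity grade. Section 6.2.3 requires altered consciousness and active treatment by another person. Section 6.2.4 requires symptoms, ketones, pH or bicarbonate, and treatment in a health care facility. Judgement remains in whether impairment made assistance necessary, and in the allowance that DKA criteria may be deemed probably met on the available data.
- *CGM endpoints (secondary 2 to 5).* These are device-measured and unaffected.

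**Step 3. Where a disagreement goes.** It goes to HDEC under 6.5 and nowhere in Chapter 8.

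**Step 4. Illustration of one changed label.** The event counts are assumed. The denominators are the 10-completer goal and the maximum of 20 consented. Exact (Clopper-Pearson) 95% limits:

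- For 0 of n, the upper limit is 1 − 0.025^(1/n). For n = 10 this is 1 − 0.6915 = 30.8%; for n = 20 it is 16.8%.
- For 1 of n, the lower limit is 1 − 0.975^(1/n), which is 0.25% for n = 10 and 0.13% for n = 20. The upper limit is the 97.5% quantile of Beta(2, n − 1), which is 44.5% and 24.9%.

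At n = 10, one participant with a device-related event is 10% (0.3% to 44.5%). Relabelled as unrelated, the result is 0% (0% to 30.8%). At n = 20 the same change is 5% (0.1% to 24.9%) to 0% (0% to 16.8%). The intervals overlap heavily, so the change that matters is from an event seen to none seen.

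**The case against.** A sponsor-employed medical monitor is not in itself a fault, and the rule is openly stated. Three stronger readings are tempting, and the documents do not support them.

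- **That the sponsor's officer alone decides the primary result.** A relatedness decision cannot remove a severe hypoglycemia or DKA event from the primary count. Removing one would mean reclassifying the type of event against the written criteria in 6.2.3 and 6.2.4.
- **That the override works in one direction.** Sections 6.2.5 and 6.5 are symmetric: the Medical Monitor may upgrade an event as well as downgrade it. The assessor has an interest, but the rule has no direction.
- **That events would be hidden.** Discrepancies go to HDEC. The principal investigator separately reports serious study-related events (6.4). One severe hypoglycemia or DKA event ends that participant's device use (6.6.1). A reportable adverse event relabelled as unrelated still appears in the 8.1 tabulation. One gap remains: under 6.2.2, milder glucose events are recorded as adverse events only if tied to a device effect or to stopping the device. The documents do not say how a disagreement on that tie is handled.

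Two further objections stand. The 1/10 versus 0/10 contrast would look the same under any adjudicator, so it shows sensitivity to one label and does not measure bias. The safety management plan cited in 6.5 was not supplied and may add procedure. However, the protocol itself already settles whose decision is used.

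What survives is narrower: the investigator's differing view, already collected, has no route into the results.

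**Conclusion.** The point holds as a cheap improvement to the reporting of safety. An interested assessor who knows the device has the final classification for safety endpoints and publications, and no planned output shows where the investigator differed. The exposure is direct for device-related adverse events. For severe hypoglycemia and DKA it is limited to the judgement left in their criteria, and for the CGM endpoints it is nil.

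The effect is on the credibility of a descriptive safety summary, since the plan has no error rate to inflate. The documents give no disagreement rate, so its size cannot be estimated; the intervals above are illustrative. The conclusion assumes that the endpoint uses the related/unrelated cut of 6.2.5, that the Medical Monitor knows the device (which follows from the single-arm design with no masking described), and that the safety management plan does not already require disagreements to be published.

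**What to change.** Keep the Medical Monitor's classification as the stated primary one, and change two sections.

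- **Section 8.4.** Tabulate device-related adverse events for each period, as events and as participants, once by the Medical Monitor's classification (primary) and once by the investigator's recorded assessment. State the cut that defines device-related, and use the same one in both columns. Show severe hypoglycemia and DKA in the same two ways if their classifications differ.
- **Section 6.5.** Add that every disagreement will be listed in the study results with both assessments, in addition to the existing report to HDEC.

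Counting an event whenever either assessor does is not recommended. It can only raise counts, and it would set the endpoint tables against regulatory reports and labeling, which follow the Medical Monitor.

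The cost is wording in two sections, one extra table column and a short listing. No new data, staff or participants are needed. The downside is that the reported counts may look slightly less favourable. If the assessors always agree, the two columns match and the safety summary is more convincing.
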